3.1 DESCRIPTION OF THE STUDY

This is a Phase II, multicenter, OLE study to evaluate the long-term safety and efficacy of GDC-0853 in patients with RA who have completed 12 weeks of study treatment in Study GA29350. The population for this study consists of patients with RA who have had an inadequate response to previous MTX therapy (Cohort 1 of Study GA29350) or previous TNF and MTX therapy (Cohort 2 of Study GA29350).

This OLE study will be conducted in centers that have participated in the double-blind, Phase II Study GA29350. The maximum number of patients potentially enrolling in this study will be approximately 580 patients. Patients will be assigned the same patient number they had in Study GA29350.

Eligible patients from Study GA29350 who elect to participate will receive treatment with GDC-0853 at 200 mg BID in an open-label fashion for 52 weeks, followed by a safety follow-up period of 8 weeks. Dose reductions of GDC-0853 to 200 mg QD are allowed for specific safety reasons (see Section 5.1.2) and may be allowed on the basis of clinical safety concerns of the investigator, only after discussion with the Medical Monitor. Eligible patients will be enrolled directly into Study GA30067 following treatment completion at Week 12 of Study GA29350 (e.g., they will not undergo the 8 weeks of safety follow-up in Study GA29350). The dose and route of administration of MTX at the end of the blinded Study GA29350 should be continued and held stable for the first 12 weeks of the OLE study. Discontinuation of MTX or alteration of the MTX dose prior to Week 12 is discouraged. Use of additional DMARDs other than MTX is discouraged prior to Week 12.

At Week 12, if there has not been at least a 20% improvement in the swollen joint count (SJC) and tender joint count (TJC) relative to the patient's baseline joint counts in the blinded Study GA29350, then therapy should be escalated *or substituted* per the investigator's judgment. Such changes may include an increase in the dose of MTX, addition of other DMARDs (e.g., hydroxychloroquine or sulfasalazine), substitution of MTX with leflunomide, and/or an increase in the dose of corticosteroids (see Section 5.1). The investigator may adjust the therapy (e.g., escalate or reduce) on the basis of his or her overall clinical assessment of the patient. However, certain medications, including but not limited to mycophenolate, biologics, Janus kinase (JAK) inhibitors, and calcineurin inhibitors, are prohibited throughout the OLE Study (see Section 4.3.2). Adjustment of MTX, other DMARDs, or corticosteroids for safety reasons is allowed throughout the trial (see Section 4.3.1.1).

At Week 24 in Study GA30067, if there has not been at least a 20% improvement in the SJC and TJC relative to the patient's baseline joint counts in the blinded Study GA29350, the patient should be discontinued from this study due to lack of efficacy of GDC-0853.

See Section 5.3.5.9 for adverse event reporting in the event of an unanticipated worsening of SJC and TJC.

Patients who are receiving concomitant MTX will also receive a stable dose of folic acid given as either a single dose or divided into daily doses to achieve at least 5 mg of folic acid per week.

[figure not shown]
Stable oral corticosteroids (i.e., ≤10 mg/day prednisone equivalent) are allowed at entry into the study. Maintaining a stable dose of oral corticosteroids between the time of entry up to Week 12 is encouraged. However, at any time during the study, patients who have worsening RA may receive concomitant therapy with oral or intra-articular corticosteroids (see Section 4.3.1.1) at the discretion of the investigator. Starting at Week 12, doses of corticosteroid, MTX, or both may be modified (e.g., increased or tapered) based on the investigator's clinical assessment of the patient. It is strongly encouraged that the corticosteroid dose not exceed 10 mg/day of prednisone or equivalent. Adjustment for safety reasons is allowed throughout the trial (see Section 4.3.1.1.4).

Since patients enrolling in this study may be receiving GDC-0853 for the first time, all patients will be monitored closely with more frequent visits at the beginning of this OLE study (i.e., *more frequent visits* up to Week 12 and then every 3 months, thereafter). Patients will have safety and clinical efficacy assessments at Weeks 0, 4, 8, 12, 24, 36, and 52 (see Figure 1).

Following completion of the 52-week treatment period, there will be an 8-week safety follow-up visit.

Throughout this OLE study, patients will be monitored for safety by recording adverse events, ECGs, and clinical laboratory evaluations. Efficacy and safety data will be collected at least every 4 weeks for the first 3 months and then approximately every 12 weeks thereafter until the safety follow-up visit. Safety monitoring will also be performed routinely by the IMC.

Figure 1 Study Schema

BID=twice daily; IR=inadequate response; MTX=methotrexate; OLE=open-label extension; TNF=tumor necrosis factor.

Eligible patients from the blinded study (GA29350) will be enrolled to receive GDC-0853 in this OLE study (GA30067). This study consists of 2 parts: A 52-week open-label treatment period and an 8-week safety follow-up period.

At study visits during the OLE treatment period, the morning dose of oral GDC-0853 will be administered in the clinic on Weeks 0, 4, 8, and 12 after pre-dose study assessments.

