Stable oral corticosteroids (i.e., \leq 10 mg/day prednisone equivalent) are allowed at entry into the study. Maintaining a stable dose of oral corticosteroids between the time of entry up to Week 12 is encouraged. However, at any time during the study, patients who have worsening RA may receive concomitant therapy with oral or intra-articular corticosteroids at the discretion of the investigator. Starting at Week 12, doses of corticosteroid, MTX, or both may be modified (e.g., increased or tapered) based on the investigator's clinical assessment of the patient. It is strongly encouraged that the corticosteroid dose not exceed 10 mg/day of prednisone or equivalent. Adjustment for safety reasons is allowed throughout the trial.

Since patients enrolling in this study may be receiving GDC-0853 for the first time, all patients will be monitored closely with more frequent visits at the beginning of this OLE study (i.e., *more frequent visits* up to Week 12 and then every 3 months, thereafter). Patients will have safety and clinical efficacy assessments at Weeks 0, 4, 8, 12, 24, 36, and 52.

Following completion of the 52-week treatment period, there will be an 8-week safety follow-up visit.

Throughout this OLE study, patients will be monitored for safety by recording adverse events, ECGs, and clinical laboratory evaluations. Efficacy and safety data will be collected at least every 4 weeks for the first 3 months and then approximately every 12 weeks thereafter until the safety follow-up visit. Safety monitoring will also be performed routinely by the Internal Monitoring Committee.

Number of Subjects

The maximum number of patients potentially enrolling in this study will be approximately 580 patients.

Target Population

Inclusion Criteria

Patients must meet the following criteria for study entry:

- Age 18 to 76 years
- Able and willing to provide written informed consent and to comply with the requirements of the protocol
- Completion of treatment period through Day 84 as specified in Study GA29350
- Acceptable safety and tolerability during Study GA29350 as determined by the investigator or Medical Monitor
- Have not received any prohibited medications in Study GA29350
- While taking MTX, must be willing to receive oral folic acid (at least 5 mg/week)

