4.3.1.1 Use of Treatments for Rheumatoid Arthritis

The investigator must use the procedures outlined below in making modifications to these medications and document all changes in the eCRF. If necessary, unscheduled safety laboratory samples may be collected at the discretion of the investigator to monitor for toxicity from concomitant medications (e.g., DMARDs, NSAIDs, steroids).

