4.3.1.1.4 Corticosteroids

Oral corticosteroids (\leq 10 mg/day) will be permitted during this study. If a patient was receiving background oral corticosteroids in Study GA29350, he or she should continue this same dose (\leq 10 mg/day prednisone or equivalent), which should remain stable for the first 12 weeks of the study. Starting at Week 12, corticosteroid doses may be modified (e.g., increased, tapered) on the basis of the investigator's clinical assessment of the patient. It is strongly encouraged that the dose not exceed 10 mg/day of prednisone or equivalent. Adjustment for safety reasons is allowed throughout the trial (see Section 4.3).

The use of IV or intramuscular corticosteroids is not permitted in this study.

Starting at Week 12 of this study, up to 3 intra-articular corticosteroid injections are permitted. No single injection should exceed 40 mg of triamcinolone or equivalent, and the total annual dose of intra-articular corticosteroid should not exceed 80 mg of triamcinolone or equivalent.

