4.3.1.3 Acid-Reducing Agents

Patients who use antacids (e.g., Maalox[®], Pepto-Bismol[®], Rolaids[®]) for symptomatic relief of heartburn should take GDC-0853 at least 2 hours before or 2 hours after antacid administration because GDC-0853 requires an acidic gastric environment in order to be absorbed.

Patients may be treated with PPIs or H2RAs, but should remain on a stable regimen throughout the study.

At visits with scheduled PK assessments (see Appendix 1), any use of PPIs, H2RAs, and/or *other* antacids (*e.g.*, *Maalox*®, *Pepto-Bismol*®, *Rolaids*®) should be recorded as concomitant medications, including the date and time of last administration.

4.3.2 **Prohibited Therapy**

A listing of concomitant medications that is prohibited or should be used with caution because of potential drug-drug interactions is provided in Appendix 3.

Intravenous, intra-articular, or intramuscular corticosteroids; biologic response modifiers; tofacitinib or other JAK inhibitors; and medications listed below are not allowed during this study and any use will require discontinuation of GDC-0853.

Use of the following therapies is prohibited during the study, unless otherwise specified below:

- Investigational therapy other than study drug
- Abatacept
- Adalimumab
- Anakinra
- Anti-TNF inhibitors (infliximab, etanercept, golimumab, certolizumab, or biosimilar equivalents)
- Chlorambucil
- Cyclophosphamide
- Cyclosporine
- Immunosorbent column
- Intravenous or intramuscular steroids
- Mycophenolate mofetil
- Mycophenolic acid sodium
- Oral anticoagulants, including but not limited to warfarin, dabigatran, rivaroxaban, apixaban
- Anti-platelet agents, e.g. clopidogrel (Note: NSAIDs and low-dose aspirin are acceptable.)
- Heparin, LMWH
- Penicillamine
- Rituximab (or biosimilar equivalent)
- Sirolimus
- Tacrolimus

- Tocilizumab and other anti-IL6R or anti-IL6 agents
- Tofacitinib and other JAK inhibitors
- All biosimilar agents

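### Section 4.3.2 requires GDC-0853 to be stopped after an intra-articular steroid injection that Section 4.3.1.1.4 permits

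*Combined protocol and SAP*

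**What the plan says.** The current protocol text treats intra-articular corticosteroid in these places:

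- **Section 3.1** says "at any time during the study, patients who have worsening RA may receive concomitant therapy with oral or intra-articular corticosteroids", at the investigator's discretion, with a pointer to Section 4.3.1.1. The **synopsis** gives the same permission, "concomitant therapy with oral or intra-articular corticosteroids at the discretion of the investigator", without the pointer.
- **Section 4.3.1.1** states: "The investigator must use the procedures outlined below in making modifications to these medications". Under it, **Section 4.3.1.1.4** says "Starting at Week 12 of this study, up to 3 intra-articular corticosteroid injections are permitted", and adds "No single injection should exceed 40 mg of triamcinolone or equivalent, and the total annual dose of intra-articular corticosteroid should not exceed 80 mg" (triamcinolone or equivalent). The routes it bars are two others: "The use of IV or intramuscular corticosteroids is not permitted in this study".
- **Section 4.3.2**, in the sentence after the reference to Appendix 3, says "Intravenous, intra-articular, or intramuscular corticosteroids; biologic response modifiers; tofacitinib or other JAK inhibitors; and medications listed below are not allowed during this study", and then that any use means stopping GDC-0853. The bullet list that follows names only intravenous and intramuscular steroids.
- **Section 4.5.2** includes medication prohibited under Section 4.3 in its list of compulsory reasons to stop treatment. Such patients have an early termination visit and 8 weeks of safety follow-up, and are not replaced.
- **Section 4.4.5.1.1** has an injected joint recorded as not done for 12 weeks, after which it may be assessed again.

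**The concern.** From Week 12 the same injection is permitted rescue under one section and a compulsory reason to stop study drug under another. A site that applies 4.3.2 literally would end treatment in a patient who was managed exactly as 4.3.1.1.4 allows.

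Two things are at stake. The primary objective is safety over up to 52 weeks of treatment, and each such stop removes the rest of that patient's exposure. The primary efficacy endpoint is ACR50 at Week 52, and the patient would have no on-treatment assessment at that visit. Sites reading different sections would also classify the same event differently. That would affect the summaries of withdrawal reasons and major deviations (Section 6.2) and the per-protocol set, which leaves out major violators (Section 6.5).

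**Working it through.** The plan states no figure on this point, so the check is mainly a comparison of texts, followed by simple arithmetic on the size per patient.

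**1. The rules side by side**

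| Place | Intra-articular injection | Consequence of use |
|---|---|---|
| Synopsis, 3.1 | Allowed at any time for worsening RA | None stated |
| 4.3.1.1.4 | Up to 3, from Week 12, within dose limits | None stated |
| 4.3.2 (prohibition sentence) | Not allowed | GDC-0853 stopped |
| 4.3.2 (bullet list) | Not listed | – |
| 4.4.5.1.1 | Rule for scoring the injected joint | Joint not counted for 12 weeks |

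From Week 12, 4.3.1.1.4 therefore allows up to 3 injections (80/40 = 2 if each is at the single-dose maximum) and the 4.3.2 sentence allows 0.

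**2. Whether the text reconciles them**

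- The exception clause in 4.3.2 introduces the bullet list and refers to what follows it. The permission in 4.3.1.1.4 comes earlier and is not covered.
- The pointer in 3.1 to 4.3.1.1 can bring the Week 12 limits into 3.1. It does nothing about 4.3.2.
- The protocol states no rule that a specific section overrides a general one.

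**3. Which text is the outlier**

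The bullet list in 4.3.2 and the bar in 4.3.1.1.4 both name only the intravenous and intramuscular routes. Section 4.4.5.1.1 assumes that injected patients go on being assessed, and the synopsis and 3.1 treat the route as allowed. The single word in the 4.3.2 sentence is the likely error, although the documents do not settle this.

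**4. Size per affected patient**

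Inputs: 52 planned treatment weeks (3.1); drug stopped at the injection in week *t*; patient would otherwise complete treatment. Weeks lost = 52 − *t*.

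- Week 12: 52 − 12 = 40 weeks, 40/52 = 77%
- Week 24: 52 − 24 = 28 weeks, 28/52 = 54%
- Week 36: 52 − 36 = 16 weeks, 16/52 = 31%

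These are upper bounds. Sections 3.1 and 4.5.2 end treatment at Week 24 without a 20% improvement in both joint counts. For a patient who would fail that rule, a Week 12 stop costs 24 − 12 = 12 weeks and a Week 24 stop costs 24 − 24 = 0. Such a patient would have had no on-treatment Week 52 assessment in any case.

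**5. What remains observed**

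Appendix 1 schedules joint counts and the other ACR components at the early termination visit, so the patient's status when treatment stops is recorded. It is not a Week 52 value.

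**6. What cannot be derived**

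The documents give no injection rate, so the number of patients affected is unknown.

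**The case against.** The strongest reply is that this is a one-word slip with an obvious answer. Every other relevant passage treats the injection as allowed, and a sensible site would follow the detailed section or ask the Medical Monitor. It is indeed not known whether any site would follow the 4.3.2 sentence. But that sentence is the one that carries a compulsory consequence, and 4.5.2 backs it, so a cautious site could reasonably obey it.

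A second reply is that little rests on it statistically. Section 6 plans no tests and summarizes efficacy descriptively. The safety population keeps everyone who took a dose, and the intent-to-treat summary keeps all eligible enrolled patients. This stands as far as it goes: no inference is invalidated. Keeping a patient in the denominator does not restore the lost exposure or the Week 52 observation.

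Several stronger readings are tempting, and the documents do not support them:

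- *Three irreconcilable rules.* The synopsis, 3.1 and 4.3.1.1.4 are permissions, and 3.1 points to the section that holds the limits. The difference between any time and Week 12 is loose summary wording, secondary to the clash with 4.3.2.
- *A forced stop wholly unrelated to efficacy.* In the synopsis and 3.1 the trigger for an injection is worsening RA, which is an efficacy matter.
- *A matching conflict for oral steroid.* Section 3.1 encourages a stable dose and 4.3.1.1.4 says it should stay stable. Both are advisory, and the silence of 4.3.1.1.4 does not cancel the exception for worsening disease in 3.1.

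**Conclusion.** The conflict between 4.3.1.1.4 and the prohibition sentence of 4.3.2, reinforced by 4.5.2, is real in the current text and should be corrected. Confidence is high about the wording and much lower about how often it would matter.

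The per-patient loss of at most 40, 28 or 16 weeks rests on three assumptions: the site applies 4.3.2 as written, the drug stops at the injection, and the patient would otherwise have completed 52 weeks. The third fails for anyone who would stop at Week 24 for lack of efficacy.

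A reader might infer a bias in ACR50 in a known direction. The documents do not support that. A forced stop loses the on-treatment Week 52 result, while a patient who continues after an injection may improve in CRP, pain or other joints. Leaving the injected joint uncounted for 12 weeks is only a partial safeguard. The net direction is unknown.

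**What to change.** 1. Delete *intra-articular* from the prohibition sentence in Section 4.3.2, so that it agrees with its own bullet list, Section 4.3.1.1.4 and Section 4.4.5.1.1. Section 4.5.2 then needs no change.
2. Have the sponsor confirm when injections may start, and use the same wording in the synopsis, 3.1 and 4.3.1.1.4. The choice belongs to the sponsor. A Week 12 start fits the aim in 3.3.5.3 of stable concomitant medication up to the Week 12 efficacy assessment, but a patient who flares earlier could not have an injection. An earlier start keeps that rescue and accepts some disturbance of the Week 12 assessment. Section 3.3.5.3 only encourages stability, so it does not force the answer.

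The cost is amendment wording in a few places, with no new visits, data or analyses.

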3.1.1 Internal Monitoring Committee

Periodic safety reviews for this OLE will *also* be performed by the Sponsor's IMC as outlined in the IMC Charter. *If necessary, cumulative unblinded data for patients remaining in the parent study may also be made available to IMC members.* This committee will be unblinded to treatment assignments from the parent Study GA29350 and will include a clinical scientist, drug safety scientist, biostatistician, and statistical programmer from the Sponsor. The IMC members will not have direct contact with investigational staff or site monitors. The IMC may request that additional Sponsor scientists participate in the data analyses and review.

3.2 END OF STUDY AND LENGTH OF STUDY

3.2.1 Length of Study

[figure not shown]
The maximum time in the study for a patient is 60 weeks, including treatment for 52 weeks and an 8-week safety follow-up period after the last dose of GDC-0853.

3.2.2 End of Study

The end of this study is defined as the date when the last patient, last visit (LPLV) occurs or the date at which the last data point required for statistical analysis or safety follow-up is received from the last patient, whichever occurs later. LPLV is expected to occur approximately 60 weeks after the last patient is enrolled.

3.3 RATIONALE FOR STUDY DESIGN

3.3.1 Rationale for GDC-0853 Dose and Schedule

In the event of a safety issue, dose reduction to 200 mg QD is permitted (see Section 5.1.2). This dose was selected because it is expected to reflect what may be a physician-initiated dose reduction in a real-world clinical setting (i.e., changing the dosing interval from BID to QD).

No safety or tolerability issues were identified in healthy subjects receiving GDC-0853 up to 600 mg in the single-dose Study GP29318 (SAD) and up to 250 mg BID and 500 mg QD for 14 days in the multiple-dose study GA29347 (MAD). No maximum tolerated dose was identified, and there were no dose-limiting adverse events; all adverse events were Grade 1 (mild) and transient.

Data from experiments evaluating the PD effects and anti-inflammatory activity of a tool BTK inhibitor compound (GDC-0834) in the rat model of CIA suggest that the amount of BTK inhibition anticipated in this study may be sufficient to achieve meaningful anti-inflammatory activity. These studies suggest that 70% BTK inhibition, as measured by phospho-BTK inhibition, is required for half-maximal activity (Liu et al. 2011). However, it is not known whether BTK inhibition in the rat CIA model accurately predicts efficacy in human RA.

Dose levels in this study are anticipated to result in exposures below 10 μ M • h (mean AUC₀₋₂₄), which is the NOAEL from nonclinical toxicology studies. The NOAEL (10 μ M • h) was defined in the 4-week dog study by vasculitis at higher doses (\geq 56 μ M • h). In the ongoing 9-month dog study, no vasculitis was observed up to the highest dose tested (37 μ M • h); however, 1 of 4 dogs at the highest dose had seminiferous tubule degeneration in the testis; a 4-month recovery phase is in progress. No testicular findings have been observed at lower doses (\leq 10 μ M • h). For further details, see the GDC-0853 Investigator's Brochure.

3.3.2 Rationale for Open-Label Design

The primary objective of Study GA30067 is to understand the long-term safety of GDC-0853 over an extended treatment period of up to 52 weeks. The open-label study design will allow all eligible patients originating from the blinded Study GA29350 to be treated with GDC-0853.

3.3.3 Rationale for Biomarker Assessments

Biomarker assessments, before and at various timepoints after treatment, will be used to advance the understanding of the mechanism of action (MOA) of GDC-0853 in patients with RA, define PK/PD relationships, and aid dose regimen selection for future studies. A biomarker that predicts response to GDC-0853 would be valuable to patients and treating physicians as an aid in identifying patients with increased likelihood to achieve clinical benefit, thus guiding treatment decisions.

3.3.4 Rationale for PK Sample Collection Schedule

The PK sampling schedule consists of predose assessments at multiple visits, which will enable the estimation of GDC-0853 exposure as well as an evaluation of intrapatient variability over the 52-week dosing period. In addition, these results will contribute to the understanding of the GDC-0853 exposure-response analysis, which will assist in characterizing how safety and efficacy are impacted by drug exposure.

